**1. Abstract:**

Black women have the highest prevalence of obesity in the U.S. with more than half (56.6%) of Black women experiencing obesity. This disease increases the likelihood of having diabetes and other chronic diseases, and decreases quality of life and life expectancy. The U.S. Preventive Services Task Force recommends that all adults who have obesity participate in an evidence-based, intensive, multicomponent behavioral treatment for this disease. Such treatment has been shown to produce clinically significant weight-loss among patients; however, this weight-loss is typically not sustained over time. Health care professionals nationally agree that treatment of obesity should be occurring and evaluated in primary care settings.

We will test the effectiveness of a culturally sensitive, evidence-based, multi-component, behavioral program for treating obesity called Health-Smart.TM This program will be implemented for 6 months in 20 UF Health Jacksonville primary care clinics by Community Health Workers (CHWs) with Black women patients who have obesity, and followed by either of two physician-implemented behavioral counseling weight loss maintenance programs that are applied quarterly over 12 months to prevent weight gain. Specifically, we will compare the effects on weight-loss and weight-loss maintenance of (1) Health-Smart

***plus*** the Patient-Centered, Culturally Sensitive Weight Loss Maintenance Program (PCS-WLM), and (2) Health-Smart ***plus*** the Standard Behavioral Weight Loss Maintenance Program (SB-WLM). We expect that (a) the PCS-WLM will result in significantly greater weight-loss and weight-loss maintenance compared to SB-WLM, and (b) that the model used to integrate CHWs into the health care team at each clinic will result in high ratings of this integration by the CHWs and other clinic staff involved with this study.

## **2. Background:**

Obesity has been called a modern epidemic. Obesity increases the likelihood of experiencing various chronic diseases such as diabetes, hypertension, coronary heart disease, and some cancers, all of which negatively impact quality of life. Thus, reducing and eventually eliminating obesity continues to be a national health priority.

Approximately 75% of non-Hispanic Blacks are overweight or obese. This percentage is higher than other US racial and ethnic groups. The 2011-12 US National Health and Nutrition Examination Survey revealed that (a) the prevalence of obesity ( $BMI \geq 30 \text{ kg/m}^2$ ) had increased to 34.9% and (b) this obesity increase was even higher among Blacks (47.8%) and Hispanics (42.5%). Black and Hispanic women are affected by obesity more than their male counterparts. Notably, Black women (BW) have the highest obesity prevalence in the US. More than half (56.6%) of BW are obese, compared to 44.4% of Hispanic women and 32.8% of non-Hispanic White women. Despite the high prevalence of obesity among BW, they have been underrepresented in weight-loss trials and weight-loss maintenance studies.

Numerous reviews have found that lifestyle interventions are effective in helping individuals lose weight. Generally, lifestyle interventions that are delivered in weekly group sessions over 4 to 6 months can help individuals achieve weight losses of approximately 5 to 10% of their body weight. Unfortunately, many individuals who successfully lose 5% or more of their body weight gradually regain most, if not all, of the weight they lost. Thus, the real goal of obesity treatment should be to help individuals achieve weight loss and keep the weight off over the long-term.

Accordingly, several obesity researchers have called for a focus on preventing weight regain, particularly in primary care settings. The Obesity Reduction Black Intervention Trial (ORBIT) provides important insights into weight loss and maintenance for BW. The 6-month weight-loss intervention in this trial was implemented by trained interventionists and involved twice-weekly group discussions focusing on eating a healthy diet, restricting calories, and increasing physical activity and related goals, plus monthly 30-minute motivational interviewing (MI) sessions by the interventionists. The 12-month weight-loss maintenance intervention in the ORBIT study included group sessions that decreased in frequency plus monthly MI sessions. At the end of the 6-month intervention period, the intervention group had lost 3.0 kg, and the control group had gained 0.2 kg. Both groups gained weight between months 6 and 18 (1 kg in the intervention group and 0.1 kg in the control group). At month 18, only 24% of the intervention group and 12% of the control group had lost at least 5% of their initial body weight. The authors of the article reporting these findings concluded that the low weight-loss and unsuccessful weight-loss maintenance indicates that more research is needed to identify what contributes to meaningful weight loss and weight-regain prevention in BW.

### 3. Specific Aims:

The project has three primary aims. The **first primary aim** is to evaluate the effectiveness of the Community Health Worker (CHW)-implemented, clinic-located, evidence-based, 6-month Health-Smart weight-loss program as indicated by (1) participating patients' mean weight loss and (2) percentage of participating patients who show clinically significant weight loss (i.e., at least 5% of baseline body weight).

The **second primary aim** is to compare the outcomes of two 12-month, clinic-based weight-loss maintenance programs implemented by patients' respective physicians after the 6-month weight-loss intervention. The first program is the Patient-Centered, Culturally Sensitive, Weight-Loss Maintenance (PCCS-WLM) program, which is a weight-maintenance program implemented by physicians who receive patient-centered, cultural sensitivity training to enhance their ability to talk with patients about weight-loss issues in ways that enable patients to feel comfortable with, respected by, and trusting of their physicians. The second program is a standard behavioral weight-loss maintenance (SB-WLM) program that is recommended by the Institute of Preventive Medicine. The specific patient reported outcome measures related to this aim are continued weight loss or maintaining weight loss and changes in patients' perceived levels of (a) satisfaction with physician care, (b) provider cultural sensitivity, and (c) physician engagement in discussions of their weight and health-smart behaviors (e.g., eating and physical activity).

The **third primary aim** is to implement and evaluate a Medical Assistant (MA)-led program designed to integrate trained CHWs into the health care team in 20 primary care clinics so that these CHWs can implement the 6-month Health-Smart weight-loss program with BW patient participants who have obesity at these clinics. MAs at each participating clinic will train and mentor the CHWs assigned to the clinic to become integrated into the health care team at that clinic. This training will be informed by the nationally-recognized TeamSTEPPS Program—an evidence-based set of teamwork strategies and tools developed by the Agency for Healthcare Research and Quality (AHRQ) aimed at optimizing patient outcomes by improving communication and teamwork skills among health care professionals. CHW integration effectiveness will be assessed using (a) ratings by CHWs, MAs, and physicians in the proposed study on the relevant subscales of a TeamSTEPPS team integration assessment tool, the AHRQ Office Survey for Patient Safety.

The **secondary study aims** are to determine if, at the end of the 12-month weight-loss maintenance programs, there are differences in the following participant health indicators in association with type of physician-implemented weight-loss maintenance program implemented by the participating patients' physicians: (a) blood pressure, lipids, HbA1c, and blood glucose; (b) healthy eating and physical activity engagement; (c) participant-perceived barriers to health-smart behaviors; and (d) health-related quality of life.

The **primary hypotheses** that will be tested are the following: (1) at the end of the 6-month Health-Smart weight-loss intervention, participating patients will show weight reduction of at least 5% of their baseline weight, and (2) at the end of 18 months, a significantly larger percentage of participants at clinics assigned to the 12-month PCCS-WLM program will maintain initial weight loss or show continued weight loss compared to participants at clinics assigned to the 12-month SB-WLM program.

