**Participation in the 6-month Health-Smart weight loss program.** Within two months after completing Measurement Session 1, patients will begin the Health-Smart weight loss program. ***The 6-month clinic-adapted Health-Smart intervention is part of both comparators*** and includes the following components/strategies: (a) assessment of each

participant's motivators of and barriers to health-smart behaviors using the Motivators of and Barriers to Health-Smart Behaviors Inventory—which has been published by the study PI; (b) coaching by a trained CHW that involves using the inventory-identified motivators and barriers to facilitate the patient participant's goal-setting and identification of strategies to achieve their goals, teaching participants to monitor selected health-smart goals and related goal attainment strategies, reviewing the standard goals for all patients that include 5% weight loss and increasing or maintaining steps walked to meet the 10,000 steps per day walking goal, and facilitating a patient-family member/friend discussion during which the patient asks the family member/friend to engage in behaviors that will support the patient in implementing her health-smart goal achievement strategies; (c) three months of weekly group sessions and then 3 months of bi-weekly group sessions; (d) 150 minutes of physical activity each week via patient participant-arranged or CHW-arranged activities such as group walks and individual walking to achieve 10,000 steps per day, and/or other self-selected moderate physical activities, and documentation of the physical activities in addition to documenting steps walked. Furthermore, the walking steps should begin with any number of steps that can be walked without any physical discomfort (e.g., pain, difficulty breathing) and then gradually increased by a number of steps that can be walked without any physical discomfort. Additionally, for participants who cannot walk at all, the physical activity goal is to engage in any physical activity up to 150 minutes per week that does not cause any physical discomfort. During at least one of the sessions in the Health-Smart intervention, patient participants will be given the opportunity to anonymously or directly ask health-related questions to a panel of health experts (e.g., dietitians) and Black women community members who have lost weight and maintained this weight loss.

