## 5. Statistical Analysis

The primary outcome is change in body weight (weight loss and maintenance of weight loss) in BW patient participants at the 20 participating primary care clinics. The unit of randomization will be the primary care clinic. Each clinic will be randomized into one of the two weight loss maintenance conditions (PCCS-WLM and SB-WLM).

**Sample Size/Power.** To detect a weight-loss difference of 5 pounds (between two groups) with a standard deviation of 12.5 pounds with 80% power and a 5% significance level, we will include 20 clinics and 25 study participants per clinic. Based on our pilot data, an intra-class correlation of 0.05 among patients within a clinic is used in these calculations. Based on the power calculation above, a total of 500 participants (20 clinics x 25 patient participants per clinic) will be needed for final analyses. Assuming a 25% dropout rate of patients per clinic, we will need 34 patients per clinic; thus, 680 patients will be enrolled in the study. However, based on Wave 1 (which involves 7 clinics) patient participant drop-out rate, the number of participants per clinic will need to be increased for Wave 2 and 3 to an average of 40 patients per clinic. Thus, the maximum number of patient participants enrolled in the study will be 758. Consequently, each of the two study arms will have a maximum of 379 patient participants.

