**Data Analysis.** [name] who has a doctorate in Biostatistics will perform data analysis. Analyses begin with numerical and visual summaries of baseline characteristics of the sample. Continuous variables will be summarized by means, standard deviations, and medians. Categorical variables will be summarized by frequencies and percentages. Visual summary may include graphs, charts and tables. The main outcome variable (weight change) will be analyzed using a 2-level hierarchical model within the framework of a linear mixed model. The 2 levels of hierarchy will be defined as patient-level and clinic-level. Data will be analyzed within the context of linear mixed model. Weight loss between 6 and 18 months will be evaluated and compared between groups by defining an appropriate contrast within the model. Similarly, weight loss from baseline to 6 months also will be estimated (but not compared) by defining a contrast. It is assumed that those participants with BMIs greater than 50 will lose weight at the same rate of those with BMIs between 30 and 50. However, we plan to analyze the weight loss rates in two ways: one with all of the participants in the analysis and another with BMIs greater than 50 excluded. Based on these two analyses, we

can see if the subset of participants with BMIs greater than 50 impacts the effect size. These data sets will be compared using a mixed model for categorical data (e.g., GLIMMIX procedure in SAS). Descriptive analysis will be used to evaluate the effect of age, BMI, poverty rate (according to zip code), insurance type, and HbA1c at baseline.

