## **8. Possible Benefits**

Participants may personally benefit from taking part in this study since they will learn strategies to eat healthier, exercise more, get more rest, and manage stress and depression. They also may lose weight, which, for people with obesity, is often associated with improvements in health.

The information obtained in this study will help determine the effectiveness of Health-Smart and the physician-implemented weight loss maintenance programs for promoting and/or maintaining weight loss among Black women patients. If these interventions are found to be effective, they can be implemented at other primary care clinics with other Black women patients. Support would also be provided for testing these interventions with other women at primary care clinics who are not Black.

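### Aim 1 is worded as an evaluation of Health-Smart's effectiveness, but all participants receive the program and the 6-month change has no comparator, so it cannot be attributed to the program.

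*Combined protocol and SAP*

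**What the plan says.** Section 3 (Specific Aims) makes this a primary aim: it "is to evaluate the effectiveness of the Community Health Worker (CHW)-implemented, clinic-located, evidence-based, 6-month Health-Smart weight-loss program". The indicators are mean weight loss and the percentage of patients losing at least 5% of baseline weight. Hypothesis 1, in the same section, is that "at the end of the 6-month Health-Smart weight-loss intervention, participating patients will show weight reduction of at least 5% of their baseline weight". The Abstract and the Study Intervention paragraph of Section 4 likewise speak of testing the program's effectiveness. Section 8 (Possible Benefits) says "The information obtained in this study will help determine the effectiveness of Health-Smart and the physician-implemented weight loss maintenance programs" and adds "If these interventions are found to be effective, they can be implemented at other primary care clinics with other Black women patients".

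The design text reads differently. In Section 4, the paragraph on the 6-month program says "The 6-month clinic-adapted Health-Smart intervention is part of both comparators". Section 5 says "Each clinic will be randomized into one of the two weight loss maintenance conditions (PCCS-WLM and SB-WLM", and its Data Analysis paragraph says "weight loss from baseline to 6 months also will be estimated (but not compared) by defining a contrast". No untreated, usual-care, wait-list or historical control is described for months 0 to 6. The three enrolment waves are not presented as a source of control periods.

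**The concern.** Effectiveness is a statement about what the program adds over what would have happened without it. The randomisation carries no information on that for the first six months, because both arms are treated alike. What remains is a before-after change in women who came forward after a flyer, a letter or a conversation at the clinic, and who had to be ready to alter diet and activity (inclusion criterion 6). Their motivation, any background drift in weight, and the gap between the baseline measurement and the first session are all inside the estimate.

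What is at stake is the conclusion for one of three primary aims. Under the present wording, a 6-month mean loss or a 5% responder percentage could be written up as the effect of Health-Smart. The responder percentage needs the most care, because weight varies between women and some may cross a 5% threshold without any program.

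**Working it through.** **1. Aim set beside design**

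- Who receives Health-Smart: everyone (Section 4).
- What is randomised: the clinic, to one of two maintenance programs, 10 clinics each (Sections 4 and 5).
- Analysis of months 0 to 6: a contrast within the mixed model, not compared between groups (Section 5).
- Hypothesis 1: a fixed 5% benchmark with no control (Section 3). It is listed among hypotheses to be tested, but the Data Analysis paragraph describes estimation only and no test against 5%.
- Interval: the program may start up to two months after Measurement Session 1 (Section 4), so baseline to follow-up can run from about 6 to about 8 months.

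Nothing here identifies a difference between receiving and not receiving Health-Smart.

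**2. The plan's own power calculation**

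Inputs from Section 5: difference 5 lb, SD 12.5 lb, 80% power, 5% significance (two-sided assumed, as sidedness is not stated), ICC 0.05, 20 clinics of 25.

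- Unclustered n per arm: 2 × (1.960 + 0.842)² × 12.5² / 5² = 98.1, so 99.
- Design effect: 1 + (25 − 1) × 0.05 = 2.2.
- Required per arm: 99 × 2.2 = 217.8, against 250 planned.
- Power with 250 per arm (effective 250 / 2.2 = 113.6): 81.4% with a t distribution on 18 df, 85.4% with the normal approximation.
- Dropout: 25 / 0.75 = 33.3, so 34 per clinic and 34 × 20 = 680. With the waves: 7 × 34 + 6 × 40 + 7 × 40 = 758.

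The stated figures reproduce, but they are for a difference between two groups. They do not address Aim 1.

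**3. What the sample size gives Aim 1**

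Assume that the 12.5 lb SD and the ICC of 0.05 also apply to the 0-to-6-month change; the documents do not say so.

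- SE of the mean change: 12.5 × √(2.2 / 500) = 0.83 lb.
- 95% half-width: 2.093 (t, 19 df) × 0.83 = 1.7 lb; 1.4 to 2.1 lb for an SD of 10 to 15 lb.
- A true mean change of 3 lb, whatever its cause, would be declared non-zero with about 93% power.

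The estimate would be precise. Precision does not separate the program from the other contributions.

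**4. What the cited trial of Black women shows (Section 2)**

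- Month 6, mean change: intervention −3.0 kg, control +0.2 kg. Uncontrolled change 3.0 kg; controlled difference 3.0 + 0.2 = 3.2 kg. The uncontrolled figure is 0.2 kg smaller, so there is no inflation.
- Month 18, responders: "only 24% of the intervention group and 12% of the control group had lost at least 5% of their initial body weight". The controls' mean had by then moved by 0.2 + 0.1 = +0.3 kg. A nearly flat control mean therefore coexisted with a 12% control responder rate.
- Month 6, control responder rate: not given.

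**The case against.** The strongest reply is that the plan hides nothing. Aim 1 defines its indicators, hypothesis 1 is a fixed benchmark among participating patients, and Section 5 says outright that the 6-month loss is not compared. A single-group change described against a benchmark is a legitimate aim. Section 8 is hedged: the study will help determine effectiveness, and wider use is conditional. The exclusion criteria also remove several competing causes of weight change, such as recent bariatric surgery, weight-loss medication within 6 months, pregnancy and serious illness affecting weight. All of this stands. It makes the fault a mismatch of wording and design, not a concealed comparison. It does not remove the mismatch, because a primary aim still names a property that the design cannot show.

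Several stronger readings are tempting but not supported:

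- A reader might infer from 24% against 12% that an uncontrolled responder rate would be twice the program's effect. Those are month-18 results after a 12-month maintenance phase, in another trial. They do not measure bias in a 6-month rate here.
- A reader might infer that mean loss will be overstated. The only 6-month figures in the documents point slightly the other way.
- A reader might infer that baseline and follow-up fall in opposite seasons. With a gap of up to two months and three waves, that is not exact, and no seasonal effect is given.
- A reader might infer that the plan commits to roll-out on an uncontrolled result. The conditional wording of Section 8 does not say that.

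**Conclusion.** The concern holds as a mismatch between claim and design. The 6-month mean change and the percentage losing at least 5% cannot be attributed to Health-Smart, because no one is observed without it over that period. This follows from the documents' own description and needs no outside assumption.

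The size of the non-program component at month 6 cannot be derived from the documents, for either measure. The cited 12% supports only the statement that a control responder rate need not be near zero. The 1.7 lb half-width rests on carrying the planning SD and ICC over to the 0-to-6-month change. The randomised comparison of PCCS-WLM with SB-WLM, its power and its analysis are untouched. The change is worth making because it affects what a primary aim may conclude.

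**What to change.** Reword Aim 1, hypothesis 1 and the matching sentences in the Abstract, the Study Intervention paragraph and Section 8, so that:

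- the trial estimates, among women who receive Health-Smart, the weight change from baseline to month 6 and the percentage with at least 5% loss;
- each estimate carries a confidence interval that accounts for clustering by clinic, and Section 5 says so;
- results are described against the 5% benchmark, with no causal effectiveness claim for Health-Smart;
- the text states that PCCS-WLM versus SB-WLM is the only randomised comparison.

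This needs edits in these places and no new data. The downside is a more modest claim for Aim 1.

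Do not try to fill the gap with a 5%-loss rate from the same women's pre-enrolment clinic weights. Exclusions 3 and 6 remove recent users of weight-loss medication and women with unintentional loss of at least 5% within 6 months of enrolment. The pre-enrolment rate would therefore be held down by eligibility and would flatter the program. An interval before volunteering also cannot account for the motivation to volunteer.

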#### 4. Research Plan:

**Target Population:** The target population for this study is Black women patients with obesity and are current patients in the UF Jacksonville Primary Care Network. This population was selected because they have a high incidence of mortality due to obesity, and have the most potential direct benefit from participating in this study.

**Inclusion/Exclusion Criteria:** The participant inclusion criteria are: (1) African American/Black, (2) female, (3) age 21 years or older, (4) BMI of 30kg/m^2 or higher; (5) active patient of a participating clinic (i.e., at least 2 clinic visits in the last 24 months), and (6) willing and ready to change one's diet and physical activity level, and (7) willing to be randomized to either of the two physician-implemented weight-loss maintenance intervention groups. Exclusion criteria are (1) any serious medical condition that likely affects weight, such as end stage renal disease or cancer, (2) prior bariatric surgery within the last 5 years or plans for this surgery in the next 2 years, (3) use of prescription or over-the-counter weight-loss medication within the last 6 months, (4) currently pregnant or plan to get pregnant within the next 2 years, (5) plan to relocate from the areas served by participating clinics within the next 2 years (6) having had unintentional weight loss ( $\geq 5\%$  of body weight) within 6 months of enrollment, and (7) taking a daily dose of an oral corticosteroid or anti-psychotic (clozapine, olanzapine, or risperidone) for less than six months.

**Participant Recruitment:** Participants will be recruited from the UF Jacksonville primary care network. At least 20 of these primary care clinics will be targeted for recruitment of eligible participants, and a multi-faceted approach will be used for recruitment. At the participating clinics, recruitment will involve distribution of marketing materials (e.g., posters and flyers) in the waiting room and exam rooms. These marketing materials will include a telephone number to call if interested in the study. The participating provider in each clinic may also discuss the trial with any potentially eligible patients if they already have an appointment during the recruitment period. If a patient is initially interested in participating and appears to be eligible, the medical staff will ask the patient to complete a short form indicating that she would like to be contacted by a study team member to learn more about the trial. Additionally, to systematically identify and recruit potentially eligible participants, the research team will conduct an IRB-approved query of the UF Health-Jax electronic medical record system (Epic), and organize targeted mailings of a study participation invitation letter to potentially eligible patients (based on their age, race, sex and BMI). The letter will provide an overview of the study and the phone number to call if they are interested in participating in the study.

**Screening.** A trained research coordinator or CHW will receive the phone calls from patients who are interested in participating in the trial and will perform a screening interview after having received verbal consent from the possible patient participant (interested caller). See copy of the screening script and interview tool. If the caller meets the screening criteria and is interested in participating in the study, a visit with their physician or physician extender (ARNP or Physician Assistant) will be scheduled to ensure there are no medical contraindications to their participation in the study. This screening visit will include a review of the patient's medication inventory, medical and hospital admission history for any exclusion criteria noted above as well as a physical exam that includes measuring blood pressure, radial pulse, and weight, administering a mini-cognitive assessment, and reviewing

the patient's health history. At the end of the screening visit, patients will be informed whether or not they qualify for the study. It is estimated that approximately 1,600 individuals will need to be screened in order to enroll 758 participants. Participants will be enrolled in 3 waves: Wave 1 will include 7 clinics averaging 34 enrollees each, Wave 2 will have 6 clinics with an average of 40 enrollees each, and Wave 3 will include 7 clinics with an average of 40 enrollees per clinic. See Table 1 for wave timing.

